are no studies that have assessed the effects of 5-HTP in exercise-trained individuals. Therefore, the purpose of this investigation was to determine the effects of supplementing with 100 mg daily of 5-hydroxytryptophan (5-HTP) on indices of body composition in exercise-trained men and women.

Study Objectives

Primary Objective

To assess changed in body composition.

Secondary objective

To assess any changes in dietary intake.

Study Methods

Study Design

This study followed a placebo (PLA)-controlled, double-blind and parallel-group design.

Study population

61 physically active, healthy, adults (>18) were volunteered for this study.

Inclusion-Exclusion Criteria

Inclusion Criteria:

- Healthy or free of disease
- Minimum of 1 year of regular physical activity. Regular physical activity is defined by a minimum of 150 minutes of aerobic activity or performing muscle-strengthening exercises at least 2 days a week.

Exclusion Criteria:

- Physically inactive
- Regularly used sleep aids of any kind
- Currently taking selective serotonin reuptake inhibitors (SSRIs) and/or 5-HTP containing supplements.

Discontinuation or Withdrawal from Study

The reasons a subject may discontinue or be withdrawn from the study include, but are not limited to, adverse events, non-compliance or personal request to no longer participate in study.

Randomization and Blinding

All subjects and investigators were blinded. The supplement and placebo were in similar in capsule appearance and were packed in unmarked packaging. The research team were unaware of the subject assignments until completion of the entire study.

Intervention and Placebo

The dietary supplement (100 mg of 5-hydroxytryptophan; CLEANMOOD™) was provided by NURA™ (Irvine, California USA). CLEANMOOD is an organic 5-Hydroxytryptophan (5-HTP) ingredient. The placebo consisted of maltodextrin in a capsule. Subjects were instructed to consume one capsule daily at their convenience for 8 weeks.

Data Collection Schedule

Subjects were instructed to arrive at the laboratory after a 3-hour fast. All pre and post-testing occurred between 1200 and 1700 hours.

Protocol name: Effects of Daily Supplementation of 5-HTP on Body Composition, a Randomized Investigation
 Protocol Version 2
 Document Date: 01/03/2022
 Principal Investigators: [name] PhD FNCSA FISSN CSCS and [name] MS RD

| Study Visit | Pre/Baseline | Post |
|--|--------------|------|
| Informed Consent | x | |
| InBody | x | x |

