| Vitals | x | x |
| Supplement Instruction | x | |
| Connect MyFitnessPal account | x | |
| Asses dietary intake via MyFitnessPal | x | x |
| Asses Compliance (number of pills remaining) | | x |

Missing Data

Thirteen subjects were excluded from the data set due to lack of compliance or failure to complete the study.

Statistical Analysis

All data is presented as the mean+SD. GraphPad (Prism 8) software was used for statistical analyses. A t-test was used to determine if statistically significant differences ($p < 0.05$) existed between the delta scores of the treatment versus the placebo.

Summary of Study Data

Demographic and Baseline

The characteristics of the treatment and placebo groups were as follows (age: 5-HTP 30 ± 10 , placebo 29 ± 11 ; height cm: 5-HTP 171.0 ± 8.7 , placebo 167.7 ± 15.0 ; body mass kg: 5-HTP 72.9 ± 13.4 , placebo 69.1 ± 11.9). Subjects in this investigation were exercise-trained (years of training: 5-HTP 14 ± 10 , placebo 16 ± 11 ; hours of resistance training per week: 5-HTP 5 ± 2 , placebo 5 ± 3 ; hours of aerobic training per week: 5-HTP 5 ± 4 , placebo 6 ± 5).

FDA Annual Reporting

This study is not a FDA regulated drug or device, therefore there are no annual reporting requirements to the FDA.

Clinical Trial Data Bank

The study will be registered on <http://clinicaltrials.gov> and the NCI CTRP (Clinical Trials Reporting Program) by the Clinical Trials Office.

References

1. Birdsall, T.C., *5-Hydroxytryptophan: a clinically-effective serotonin precursor*. *Altern Med Rev*, 1998. **3**(4): p. 271-80.
2. Maffei, M.E., *5-Hydroxytryptophan (5-HTP): Natural Occurrence, Analysis, Biosynthesis,*

Protocol name: Effects of Daily Supplementation of 5-HTP on Body Composition, a
Randomized Investigation

Protocol Version 2

Document Date: 01/03/2022

Principal Investigators: [name] PhD FNCSA FISSN CSCS and [name] MS RD

- Biotechnology, Physiology and Toxicology*. Int J Mol Sci, 2020. **22**(1).
3. Halford, J.C., et al., *Serotonergic anti-obesity agents: past experience and future prospects*. *Drugs*, 2011. **71**(17): p. 2247-55.
 4. Yabut, J.M., et al., *Emerging Roles for Serotonin in Regulating Metabolism: New Implications for an Ancient Molecule*. *Endocr Rev*, 2019. **40**(4): p. 1092-1107.
 5. Cangiano, C., et al., *Effects of oral 5-hydroxy-tryptophan on energy intake and macronutrient selection in non-insulin dependent diabetic patients*. *Int J Obes Relat Metab Disord*, 1998. **22**(7): p. 648-54.

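### Adverse events are a named reason for withdrawal, but no scheduled item records them or why a subject stopped, and the 13 exclusions are reported without arm or reason

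*Combined protocol and SAP*

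**What the plan says.** - **Discontinuation or Withdrawal from Study:** the possible reasons "include, but are not limited to, adverse events, non-compliance or personal request to no longer participate in study". Adverse events are listed separately from non-compliance.
- **Data Collection Schedule:** the column heads are "Study Visit | Pre/Baseline | Post". The seven rows are consent, InBody, vitals, supplement instruction, MyFitnessPal connection, dietary intake and a pill count. Vitals are taken at both visits. The pill count, "Asses Compliance (number of pills remaining", is taken at the Post visit only.
- **Intervention and Placebo:** "Subjects were instructed to consume one capsule daily at their convenience for 8 weeks".
- **Study Objectives:** the primary objective is body composition and the secondary is "To assess any changes in dietary intake". There is no safety objective.
- **Study population and Missing Data:** "61 physically active, healthy, adults (>18) were volunteered for this study", and "Thirteen subjects were excluded from the data set due to lack of compliance or failure to complete the study". Neither the arm nor the individual reason is given, and no compliance threshold is stated.
- **Statistical Analysis:** "A t-test was used to determine if statistically significant differences" between the arms in change scores. No tabulation of events, stopping reasons or vitals is described.

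**The concern.** The plan names a category of information, adverse events leading to withdrawal, and then schedules nothing to collect it. Two consequences follow.

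First, harms of an eight-week supplement that the Background describes as raising serotonin and other brain chemicals are not systematically elicited. The Background also says that the supplement has not been studied in exercise-trained people, so tolerability in this population would be worth recording.

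Second, the excluded subjects are the group in which intolerance would most likely be found. The Background links the supplement to appetite suppression, so a reason for stopping could be related both to treatment and to change in body composition. If exclusion differed by arm for such a reason, the primary comparison in the remaining subjects could be biased. Without arm and reason, a reader cannot tell whether this is a live problem or a negligible one.

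**Working it through.** The documents give no safety figure or sample-size calculation to reproduce. The check is a reading of the schedule against the withdrawal and exclusion text, followed by arithmetic on the exclusions.

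**1. Where could intolerance be recorded?**

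| Subject | Scheduled item that could show it | Result under the text |
|---|---|---|
| Stops capsules because of a side effect, returns for Post | Pill count (no reason asked), vitals | Probably excluded for low pill use |
| Stops and does not return | None | Probably excluded as a non-completer |
| Has symptoms, keeps taking capsules | Vitals only | Analysed; symptoms leave no scheduled record |

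A subject may also volunteer a report, but no form or table is described to hold it. The results in the first two rows are inferences. With no compliance threshold or coding rule, they can be called probable and no more.

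**2. Share excluded.**
- If 61 is the number enrolled: 13/61 = 21.3%, exact (Clopper-Pearson) 95% CI 11.9% to 33.7%, leaving 61 − 13 = 48.
- If 61 is the number after exclusions: 61 + 13 = 74, and 13/74 = 17.6%.

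**3. What the split by arm could be.** Allocation is not stated, so 30 v 31 is assumed. Fisher's exact test (two-sided) compares the exclusion proportions:

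| Excluded | Proportions | p |
|---|---|---|
| 6 of 30 v 7 of 31 | 20% v 23% | 1.0 |
| 10 of 30 v 3 of 31 | 33% v 10% | 0.03 |
| 13 of 30 v 0 of 31 | 43% v 0% | <0.001 |

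All three agree with the text as written.

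**4. Possible size of the effect on the comparison (illustrative).** If k of n subjects in one arm are removed and their mean change differs by d SD from those kept, that arm's mean shifts by (k/n) × d. With n = 30 and d = 0.5 (both assumed):
- k = 7: 7/30 × 0.5 = 0.12 SD
- k = 13: 13/30 × 0.5 = 0.22 SD

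**5. What asking would show (illustrative; event rates assumed).** The probability of seeing at least one event among n subjects asked is 1 − (1 − p)^n.
- n = 30, everyone in an arm reached: 1 − 0.95^30 = 0.79 and 1 − 0.90^30 = 0.96.
- n = 24, half of the 48 remaining: 1 − 0.95^24 = 0.71 and 1 − 0.90^24 = 0.92.

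The 5% and 10% rates have no source in the documents, and the conclusion does not rest on these figures.

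**The case against.** **The misclassification is not written down.** A reader might infer that the plan codes a side-effect stop as non-compliance. It does not: the withdrawal section keeps the two reasons apart, and the Missing Data sentence summarises exclusions without setting a coding rule. This stands. What remains is that such a subject would probably still be excluded, under one description or the other.

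**Intolerance is not invisible.** A reader might infer that it could surface only through pill counts or drop-out. Vitals are taken at both visits, and a subject can give a reason when leaving. Consent pages are not in the text available, so reporting instructions there cannot be ruled out. This also stands. However, vitals are not a symptom record, and neither a volunteered report nor a consent instruction would add a schedule row, a table or a different exclusion rule.

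**Attrition can still be examined.** A reader might infer that the exclusions are beyond analysis. The protocol says that assignments became known at study completion, so the 13 can be split by arm from existing records. The documents also do not say what was recorded about each of them. The gap is therefore in what is reported, and part of it can be closed without new data.

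**Collection would seldom prove causation.** At 30 v 30 (assumed), 3 v 0 events gives Fisher p = 0.24 and 5 v 0 gives p = 0.052. This is correct, so the purpose of collecting events is description.

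**The study is not FDA-regulated.** That statement in the protocol concerns annual reporting. The protocol itself makes adverse events a withdrawal reason.

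**Conclusion.** The point holds as a gap in collection and reporting. Adverse events are a stated withdrawal reason, no schedule row collects them or the reason for stopping, and no safety summary is planned. The 13 exclusions (21% of 61, or 18% of 74 if 61 is the number after exclusions) are given without arm or reason.

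Treatment-related attrition therefore cannot be judged from what is reported. Under an assumed 30 v 31 allocation, the text allows anything from a balanced split to a clearly unequal one. The illustrative shift of 0.12 to 0.22 SD in one arm's mean depends on an assumed 0.5 SD difference and on 7 to 13 exclusions falling in that arm.

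A reader might go further and conclude that the supplement caused some of the exclusions, or that the primary result is biased. The documents support neither: nothing shows that any of the 13 had an adverse event. The plan should be corrected on this point, but the gap does not by itself invalidate the comparison.

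**What to change.** **Schedule.** Add a row, *Adverse events / reason for stopping*: one open, non-leading question at the Post visit and at any early stop.

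**Reporting.** Tabulate events, stopping reasons and the pre/post vitals already collected, by arm, for all randomised subjects.

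**Analysis.** Include excluded subjects who have outcome data in an all-randomised analysis, and keep the complier set as a sensitivity analysis. Because the pill count and the second InBody measurement share the Post visit, subjects excluded only for low pill use should have outcome data. Those who did not return will not, and their number should be given by arm.

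**If conduct is complete**, as the past tense of the Methods suggests:
- Report the 13 by arm and by any reason already on record.
- Make any late contact with them subject to IRB approval, and label the answers as retrospective recall.
- State that adverse events were not systematically elicited, and draw no tolerability conclusion.

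**Cost.** A short form, a few minutes per subject, one extra table and possibly an IRB amendment, since the protocol requires IRB approval before modifications. The by-arm report of the exclusions needs only existing records.

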5-Hydroxytryptophan (5-HTP) is an amino acid and intermediate metabolite of L-tryptophan. 5-HTP crosses the blood-brain barrier, stimulating serotonin (5-hydroxytryptamine) receptors in the central nervous system.[1, 2] Increasing serotonin levels may lead to changes in eating behavior, such as reduced calorie intake and increased satiety.[3, 4] When consumed orally, 70% of 5-HTP is delivered to the bloodstream. Once absorbed, 5HTP supplementation increases serotonin production and other brain chemicals such as melatonin, endorphins, dopamine, and norepinephrine. Supplementing with 5-HTP is linked to appetite suppression, improved sleep quality and decreased feelings of anxiety and depression. [2, 3, 5-8] 5-HTP has been posited to be an effective weight-loss aide due to its anorexigenic effects; however, little data exists and virtually all investigations have studied overweight or obese subjects. Cangiano et al. showed that 5-HTP supplementation influenced energy intake in non-insulin dependent diabetic subjects. Subjects receiving 5-HTP consumed less energy via decreased consumption of fats and carbohydrates resulting in weight loss.[5] Another study observed the effects of a 5-HTP containing supplement on body composition in overweight females. Subjects were instructed to reduce their energy intake moderately. Following 4-weeks of 5-HTP supplementation, significant reductions in BMI, arm circumference and hip circumference were observed. Increased feelings of satiety were greater in the supplement group when compared to placebo.[8] Ioannou and Williams examined the effects of 5-HTP intake on brain activity as it relates to food sensitivity in healthy individuals.[6] Subjects were randomly assigned to a 5-HTP or vitamin C supplement group. This investigation discovered that 5-HTP intake influences areas of the brain related to macronutrient selection and increased awareness of the body's internal physiological needs. The vitamin C group was more responsive to high caloric and fatty foods compared to the 5-HTP group. This study suggests that 5-HTP intake can influence macronutrient intake as well as modulate eating behaviors. Presently, there

Protocol name: Effects of Daily Supplementation of 5-HTP on Body Composition, a Randomized Investigation

Protocol Version 2

Document Date: 01/03/2022

Principal Investigators: [name] PhD FNCSA FISSN CSCS and [name] MS RD

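### The only analysis drops thirteen subjects for non-compliance or non-completion, which treatment can affect, so the comparison can be biased in either direction

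*Combined protocol and SAP*

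**What the plan says.** Under Missing Data, the combined protocol and SAP says only: "Thirteen subjects were excluded from the data set due to lack of compliance or failure to complete the study". Under Statistical Analysis it gives one test: "A t-test was used to determine if statistically significant differences ($p < 0.05$) existed between the delta scores of the treatment versus the placebo". It describes no analysis of all randomised subjects, no imputation and no sensitivity analysis. It gives no compliance threshold and no breakdown of the thirteen by arm or reason.

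Other sections bear on the point:

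- **Study population:** "61 physically active, healthy, adults (>18) were volunteered for this study". The text does not say whether the thirteen are among the 61.
- **Data Collection Schedule:** compliance is a pill count ("Asses Compliance (number of pills remaining") marked at the Post visit only. InBody is marked at that visit too.
- **Discontinuation or Withdrawal from Study:** personal request is listed, along with other grounds: "The reasons a subject may discontinue or be withdrawn from the study include, but are not limited to, adverse events, non-compliance".
- **Background:** "Supplementing with 5-HTP is linked to appetite suppression, improved sleep quality and decreased feelings of anxiety and depression".
- **Randomization and Blinding:** "The research team were unaware of the subject assignments until completion of the entire study".

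**The concern.** Randomisation makes the arms comparable as assigned. Removing subjects for something that happens afterwards keeps that protection only if treatment does not influence who is removed. Here it could. The protocol attributes effects on appetite, sleep and mood to 5-HTP, any of which might change whether a subject keeps taking capsules or returns. It also lists adverse events as a reason for leaving. Appetite is in addition the proposed route to the body-composition outcome, so exclusion could be related to both treatment and outcome.

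Two different groups are also pooled. Subjects who did not complete probably have no Post value, so their outcome is truly missing. Subjects found non-compliant by the Post pill count attended the visit at which InBody was scheduled. Their outcome would normally exist, and leaving it out is a choice.

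This is the only test of the primary objective. If exclusion is related to treatment, a significant result could partly reflect who was removed, and a null result could hide an effect.

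**Working it through.** The documents state no sample size calculation, SD of change or expected dropout, so there is no planned figure to reproduce. What follows shows how large the problem could be. It does not estimate the bias in this trial.

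**Inputs from the documents.** 13 excluded; 61 volunteers; significance at p < 0.05.

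**Assumptions.** Two-sided test; arms of 31 and 30 (no ratio is given); no true effect on body composition; SD of change equal to 1 among retained subjects in both arms; and a gap *g* of 0.5 to 1 SD between the mean change of retained and excluded subjects.

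**Size of the loss.**
- All 61 randomised, thirteen among them: 13/61 = 21.3%, leaving 48.
- 61 is the count after exclusion: 13/(61 + 13) = 13/74 = 17.6%, leaving 61.
- Some left before randomisation, for example 6: (13 − 6)/(61 − 6) = 7/55 = 12.7%.

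**Bias.** In each arm, the retained mean equals the full-arm mean plus *f·g*, where *f* is the fraction of the arm excluded. The bias in the difference is therefore

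bias = f_T·g_T − f_P·g_P.

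For example, with 10 excluded from 5-HTP and 3 from placebo and *g* = 1 in both arms: 10/31 − 3/30 = 0.323 − 0.100 = 0.223 SD. With 7 and 6 excluded and *g* of opposite sign: 7/31 + 6/30 = 0.226 + 0.200 = 0.426 SD. Reversing the sign of *g* reverses the sign of the bias.

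**Type I error.** Pooled t-test, non-central t distribution with non-centrality bias/√(1/n_T + 1/n_P), where n_T and n_P are the numbers retained:

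| Excluded (5-HTP/placebo) | Retained | Pattern of *g* | Bias, SD (*g* = 0.5 to 1) | Type I error |
|---|---|---|---|---|
| 10/3 | 21/27 | equal | 0.11 to 0.22 | 6.6% to 11.6% |
| 9/4 | 22/26 | equal | 0.08 to 0.16 | 5.8% to 8.3% |
| 8/5 | 23/25 | equal | 0.05 to 0.09 | 5.3% to 6.1% |
| 7/6 | 24/24 | equal | 0.01 to 0.03 | 5.0% to 5.1% |
| 7/6 | 24/24 | 5-HTP arm only | 0.11 to 0.23 | 6.7% to 11.9% |
| 7/6 | 24/24 | opposite | 0.21 to 0.43 | 11.2% to 30.3% |

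A simulation that excluded 7 and 6 subjects, with outcome-related exclusion in the 5-HTP arm only, gave a bias of −0.22 or +0.21 SD depending on direction and a type I error of about 13%. With random exclusion the bias was about 0 and the error 5%.

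**The 74 reading (37/37).** Opposite *g* at 7/6 gives 0.18 to 0.35 SD and 10.4% to 27.1%.

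**What the split by arm would tell us.** If treatment does not affect exclusion (hypergeometric: 61 subjects, arms 31/30, 13 excluded), a split of 8/5 or more uneven, in either direction, occurs by chance 53% of the time, 9/4 or more 21%, and 10/3 or more 5.9%. An uneven split alone would not prove bias. The last two rows of the table show that an even split alone would not rule it out.

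**Precision.** Difference detectable with 80% power (non-central t):

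| Post values recovered (61 reading) | Analysed | Detectable difference |
|---|---|---|
| 0 | 48 | 0.83 SD |
| 3 | 51 | 0.80 SD |
| 6 | 54 | 0.78 SD |
| 9 | 57 | 0.76 SD |
| 13 | 61 | 0.73 SD |

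On the 74 reading the figures are 0.73 SD as analysed and 0.66 SD if all thirteen are recovered.

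**The case against.** The strongest reply is that the bias is only conditional. The Background describes effects on appetite, sleep and mood but does not say that they cause dropout or missed capsules. The withdrawal list is generic and reports no event. The gap *g* is assumed, gaps below 0.5 SD are left out, and the 30.3% figure needs a 1 SD gap of opposite sign in the two arms with no true effect on body composition. With an equal gap and a 7/6 or 8/5 split, the error stays between 5.0% and 6.1%. All of this stands: the upper figures mark what the rule permits, and nothing suggests that they are likely.

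Blinding also helps. If the team did not know assignments until the study ended, it is unlikely to have chosen exclusions by arm, although the documents do not say whether the exclusions were settled before unblinding. Blinding does not stop treatment itself from affecting adherence or attendance.

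The remedy may recover little. Non-compliance is also a reason for withdrawal, so some non-compliers may have left before Post, and the number of usable Post values could be anything from 0 to 13. If it is 0, an as-randomised analysis rests entirely on the missing-data assumption. Disclosure by arm and reason and the sensitivity analysis would still be worth having.

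Finally, an effect among compliers can be a legitimate supportive target. The plan does not name it as its target, and it provides no as-randomised comparison beside it.

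**Conclusion.** The concern holds, and it must be fixed because this is the only analysis of the primary objective. The plan excludes subjects on post-randomisation criteria that treatment can affect and offers no as-randomised or sensitivity analysis. Confidence is high that the rule is as described and that it can bias the comparison. Whether it did so is unknown.

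With 31/30 randomised and *g* of 0.5 to 1 SD, the scenarios run from negligible to large: bias of 0.01 to 0.43 SD in either direction and type I error of 5.0% to 30.3%. The maximum is similar if 74 entered. If treatment does not affect who is excluded, the test is not systematically biased under no effect and the loss is mainly one of precision. Even then, the estimate describes compliers and completers, who may respond differently from everyone randomised. The documents do not let a reader tell which case applies.

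**What to change.** Rewrite Missing Data as follows.

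1. The primary analysis includes every randomised subject with a Post InBody value, in the assigned arm, whatever the pill count.
2. For randomised subjects with no Post value, state a missing-data method (for example, multiple imputation from arm and baseline InBody value) and a sensitivity analysis for departures from missing at random.
3. State how many were randomised to each arm and whether the 61 includes the thirteen. Tabulate the thirteen by arm and reason: non-compliant with a Post value, non-compliant without one, did not complete, adverse event. State the compliance threshold that was used and whether the exclusions were decided before unblinding.
4. Keep the complier/completer t-test as a supportive analysis.
5. The exclusions appear to have been made already, so label the revised analysis post hoc if it was specified after unblinding.

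The cost is SAP wording, one table and a re-run on whatever Post values exist. There are three downsides. Including non-compliers may dilute the estimated effect. The gain in precision depends on how many Post values exist and is nil if there are none. A post hoc label would weaken the standing of the revised result.

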Aim 2: Self-reported dietary intake will be tracked using MyFitnessPal to determine if daily 5-HTP supplementation influences eating behaviors.

Aim 3:

Methods: Subjects were randomized into a treatment (100 mg 5-HTP daily; CLEANMOOD™) or a placebo (maltodextrin). Body composition was assessed pre- and post-treatment after eight weeks via a multi-frequency bioelectrical impedance device (InBody® 270). Subjects were instructed to not change their training or eating habits; moreover, they were instructed to track their diet ~2-3 days per week using a mobile app (MyFitnessPal).

Hypothesis:

Compared to placebo, daily supplementation with 5-HTP will result in changes in body composition.

Background

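### The delta-score t-test is acceptable as a test, but the plan specifies no between-arm difference with a 95% CI, no n per arm and no baseline-adjusted estimate; all three are cheap to add

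*Combined protocol and SAP*

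**What the plan says.** The Statistical Analysis section has three elements: a presentation rule ("All data is presented as the mean+SD"), the software, and one test. The test is a t-test at p < 0.05 for whether differences "existed between the delta scores of the treatment versus the placebo". It does not mention an estimated difference between arms, a confidence interval, the number analysed per arm or a covariate.

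The primary objective is "To assess changed in body composition", and the stated purpose is to determine effects "on indices of body composition in exercise-trained men and women". The Data Collection Schedule has InBody at both visits, so every InBody outcome has its own baseline.

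On numbers, Study population says "61 physically active, healthy, adults (>18) were volunteered for this study" and Missing Data says "Thirteen subjects were excluded from the data set due to lack of compliance or failure to complete the study". The allocation ratio and the arm sizes are not given. The only baseline body-size figures with an SD are height and body mass, the latter given as "body mass kg: 5-HTP 72.9 ± 13.4 , placebo 69.1 ± 11.9".

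**The concern.** The purpose is to determine an effect, yet the only planned between-arm result is whether p falls below 0.05. In a trial of about 48 analysed subjects, a p-value above 0.05 does not tell the reader which effects have been excluded. A CI does, and it comes from the same t-test. Means and SDs of the deltas would allow a reader to rebuild it, but only with n per arm, which the documents do not give.

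Secondly, the baseline of each InBody measure is collected and enters the analysis only by subtraction. Using it as a covariate in ANCOVA can narrow the interval, and it removes the effect of chance baseline imbalance on the estimate. Whether the narrowing is worth anything depends on how strongly pre and post values correlate.

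**Working it through.** The plan states no sample size calculation, SD of change, CI or correlation, so it offers no figure of its own to reproduce.

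**Inputs from the documents.** 61 enrolled and 13 excluded, so 61 − 13 = 48 (13/61 = 21.3% lost). Baseline body mass is 72.9 (SD 13.4) and 69.1 (SD 11.9) kg.

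**Assumptions.** A 24/24 split, with 20/28 as a check; two-sided 5%, since the hypothesis has no direction; equal pre and post SDs; a pre-post correlation rho varied from 0.5 to 0.99.

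**1. Width of the t-test CI.** Half-width = t(0.975, 46) × SD of change × sqrt(1/n1 + 1/n2).
- 24/24: 2.0129 × sqrt(2/24) = 0.581 SD of change.
- 20/28: 2.0129 × sqrt(1/20 + 1/28) = 0.589 SD of change.

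In SD-of-change units this does not depend on rho. Even an observed difference of zero would leave effects up to 0.58 SD of change in either direction compatible with the data.

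**2. ANCOVA CI relative to the t-test CI.** The variance of a delta is 2σ²(1 − rho). The ANCOVA residual variance is σ²(1 − rho²). Their ratio is (1 + rho)/2. Chance baseline imbalance multiplies this by 1 + 1/44 on average, and the t quantile moves from 46 to 45 degrees of freedom (2.0129 to 2.0141).

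| rho | (1+rho)/2 × (1+1/44) | CI width ratio |
|---|---|---|
| 0.5 | 0.767 | 0.876 |
| 0.7 | 0.869 | 0.933 |
| 0.9 | 0.972 | 0.986 |
| 0.95 | 0.997 | 0.999 |
| 0.99 | 1.018 | 1.009 |

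Break-even is at rho 0.953. As rho approaches 1 the ratio tends to 1.012, so the loss is at most about 1.2%.

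**3. Illustration in kg, for body mass only.** Pooled SD = sqrt((13.4² + 11.9²)/2) = 12.67 kg. SD of change = 12.67 × sqrt(2(1 − rho)).
- t-test half-width at rho 0.90, 0.95, 0.99: 3.29, 2.33, 1.04 kg.
- ANCOVA half-width at the same values: 3.25, 2.33, 1.05 kg.
- Size of the shift in the estimate from adjusting for the 3.8 kg baseline difference, (1 − rho) × 3.8: 0.38, 0.19, 0.04 kg.

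**4. Is the 3.8 kg gap unusual?** At 24/24, SE = 12.67 × sqrt(2/24) = 3.66, t = 3.8/3.66 = 1.04, p about 0.30. If the figures describe all 61 at 30/31, p is about 0.25. Chance explains it readily.

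**5. Error rates.** Simulating no effect (100,000 trials per rho, 24 per arm, normal data), the t-test and ANCOVA each reject in about 5% at every rho. If a result counted whenever either was significant, the rate per outcome would be about 7.3%, 6.7%, 6.1%, 5.9% and 5.6% at rho 0.5, 0.7, 0.9, 0.95 and 0.99. A 95% ANCOVA CI excludes zero exactly when its p-value is below 0.05. Leaving out the second p-value therefore does not prevent this; a rule on which analysis decides does.

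**The case against.** The strongest objection is to the ANCOVA half. Its gain depends on rho, which the documents do not give. Subjects were told to hold habits constant ("Subjects were instructed to not change their training or eating habits"), and the sample mixes men and women, which widens the spread between people. Both make a high rho plausible for InBody measures. Nothing supports 0.5 or 0.7 for any of them, and for body mass at rho 0.90 to 0.99 the change in half-width is between 0.04 kg narrower and 0.01 kg wider. This stands: a precision gain is possible, not shown. The adjusted estimate still earns a place because the most it can lose is about 1% in width and it takes chance imbalance out of the estimate.

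It is also fair to say that the mean-and-SD sentence does not forbid a CI, and that the kg figures illustrate a baseline characteristic, not a named outcome. Both stand; the CI point needs neither the kg figures nor rho.

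Four stronger readings are tempting, and the documents do not support them:
- That the baseline is ignored. A delta is post minus baseline; the baseline is only not a covariate.
- That a t-test on deltas is wrong. It keeps its size and answers an objective framed as change.
- That the body-mass gap shows bias. It is compatible with chance.
- Conversely, that an acceptable test makes the result unbiased. That would need exclusions unrelated to arm and outcome. The documents do not show this for the 13 removed, some of them for non-compliance.

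**Conclusion.** A cheap improvement, not an error.

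The omission of a between-arm difference with 95% CI and n per arm is certain from the text, and its value does not depend on rho. At 48 subjects the undisclosed uncertainty is about 0.58 SD of change either side, assuming 24/24, and hardly more at 20/28.

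The case for a baseline-adjusted estimate is conditional: about 12% narrower at rho 0.5, 7% at 0.7, 1% at 0.9 and about 1% wider at 0.99, with equal pre and post SDs assumed. For stable measures the precision gain may be nil.

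The statement that the t-test holds its 5% level is limited to randomisation with complete data. A reader might infer that a CI or ANCOVA on the 48 repairs the loss of 13 subjects. It does not; that is a separate matter.

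**What to change.** 1. For each outcome, report the between-arm difference in mean change with its 95% CI from the stated t-test, and the number analysed in each arm.
2. For each InBody outcome, report beside it a baseline-adjusted difference with 95% CI, from ANCOVA of the post value on arm and the baseline of the same measure.
3. State that the delta t-test alone decides significance and that the ANCOVA is supportive. This rule is what holds the false-positive rate at 5% per outcome.
4. Label the ANCOVA post hoc if outcomes had been seen when it was added. The document is largely in the past tense and already reports group characteristics, so the label may well apply.

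**Cost.** The CI needs no new model or data. The ANCOVA costs one regression and one more reported result per InBody outcome, one degree of freedom (45 instead of 46), and an interval up to about 1% wider if rho is very high. The extra results come in a plan that names no single primary body-composition measure, which is a further reason to fix in writing which analysis decides.
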